3.4 Study Design Rationale

3.4.1 AR101 Dose Regimen and Study Periods

The dose regimen in this study is based on the dosing regimen successfully used in the phase 2 studies, ARC001 and ARC002. The ARC001 dosing regimen was based on the work of the Consortium of Food Allergy Research (CoFAR) and its investigators. The basic structure of the dose regimen consists of a 2-day initial escalation at very low doses, followed by an up-dosing phase of dose escalations with a single dose level escalation occurring every 2 weeks, and then an initial maintenance phase followed by an extended maintenance phase. This dosing regimen was well tolerated and effective in previous studies (Burks, 2012), and the 300 mg target dose was well tolerated and had clinically important activity in the AR101 phase 3 studies.

In addition, the dosing regimen to be used in this study in the Maintenance and Extended Maintenance Periods is a 300 mg dose to be administered at the dosing interval that the subject last tolerated in a previous Aimmune-sponsored clinical study.

A follow-up observation period after the last dose of AR101 is included to assess sustained clinical effect of AR101 treatment.

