For any subject having chronic/recurrent GI symptoms, especially upper GI symptoms, investigators are advised to have a low threshold for instituting a dose reduction and/or for considering early discontinuation of affected subjects from the study even if mild, owing to the potential for EoE. Further specific instructions for this AEI are provided in Section 8.1.4.2.

Dose adjustment after administration of antihistamines and/or epinephrine for allergy symptoms related to dosing is described in Section 6.10.

6.9.5 Management of Symptoms Related to Dosing Occurring During Maintenance Period (All Treatment Pathways)

Dosing guidelines following treatments given for reactions experienced by subjects in all Treatment Pathways receiving AR101 at 300 mg QD, QOD, BIW, QW, or QOW during the Maintenance and Extended Maintenance period are summarized in Table 10. A textual explanation follows the table. Dose adjustment after administration of antihistamines and/or epinephrine for allergy symptoms related to dosing is described in Section 6.10.

Table 10: Dose Adjustments Following Symptoms Related to Dosing Experienced by Subjects Receiving AR101 at 300 mg QD, QOD, BIW, QW, or QOW During Maintenance and Extended Maintenance

Treatment Regimen	Dosing Guidelines and Procedures
QD	Use up-dosing procedures (Section 6.9.3, Section 6.9.4).
QOD, BIW, QW, or QOW	For intercurrent AEs and symptoms related to dosing, hold the scheduled dose until the AE is resolved and the dose can be safely administered.
	 Reset the interval between doses once the subsequent dose is tolerated.
	 If the dose must be held for > 3 days past when the dose was due to be taken, the investigator must discuss the case with the sponsor's medical monitor prior to administering the next dose. Dosing options are described in the text following this table.
	• Subjects may be transferred to Treatment Pathway 2 anytime if impaired tolerability of the dosing regimen develops (Section 3.1.1); and they will be transferred to Treatment Pathway 2 following the occurrence of any of the following:
	- 1 related SAE
	 1 related AE graded severe
	 2 related AEs occurring on separate occasions, both graded moderate, or
	 3 consecutive doses judged "not tolerated"

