The investigator should assess the benefit-risk of continued AR101 treatment when a subject has several AR101-related systemic allergic reactions (anaphylactic events) during maintenance treatment. AE, adverse event; BIW, twice weekly; QD, once daily; QOD, every other day; QOW, every other week; QW, once weekly; SAE, serious adverse event.

- This study period consists of the subject receiving the 300 mg dose of study product QD, QOD, BIW, QW, or QOW. For any noted symptoms during the QD Initial Maintenance or Extended Maintenance period, the same study product dosing guidelines and procedures for QD dosing will be followed as for the Up-Dosing Period. However, for subjects on nondaily regimens, the following guidelines and procedures apply. The investigator should assess the benefit-risk of continued AR101 treatment when a subject has several AR101-related systemic allergic reactions (anaphylactic events) during maintenance treatment.
- The tolerability of doses on nondaily dosing regimens will be evaluated as in Section 6.8 and Table 10. In the event of a clinically significant intercurrent AE occurring at the time of a scheduled QOD, BIW, QW, or QOW dose, subjects should be advised to hold the scheduled dose until the AE is resolved and the dose can be safely administered; the interval between doses should be reset once the subsequent dose is tolerated. *If the dose must be held for > 3 days past when the dose was due to be taken*, the investigator must discuss the case with the sponsor's medical monitor prior to administering the next dose. Options available at that time include, but are not limited to, any of the following:

- ARC008 Protocol Amend 6.0
- 1. Continue the same Treatment Pathway and administer the next 300 mg dose under supervision at the study site.
 - a. If tolerated, continue EM dosing at 300 mg on the same schedule, resetting the dosing interval;
 - b. If not tolerated, consider options 2 or 3 below.
- 2. Continue the same Treatment Pathway and administer approximately half of the 300 mg dose under supervision at the study site. The entire 300 mg dose should be prepared with the preferred vehicle and then approximately half of the dose should be administered; the remainder should be discarded. If not tolerated, the subject should be discontinued from the study. If tolerated, up to 3 successive doses can be administered this way according to the subject's assigned schedule, but then 300 mg should again be attempted.

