- 3. Discontinue Treatment Pathway 1 and switch to Treatment Pathway 2, initiating the dose reduction and modified escalation procedure described in Section 7.2.2. This should be the preferred option for any QOD, BIW, or QW subject who had missed 4 or more scheduled doses and/or whose interval between AR101 exposures exceeds 14 days.
- 4. Discontinue ARC008.
- For subjects having acute reactions to QOD, BIW, QW, or QOW doses, the next action will be determined by symptom severity. As mentioned in Section 3.1.1 any Extended Maintenance subject on QOD, BIW, QW, or QOW dosing having 1 related SAE, 1 related AE graded severe, 2 related AEs occurring on separate occasions, both graded moderate, or 3 consecutive doses judged "not tolerated," will be transferred from Treatment Pathway 1 to Treatment Pathway 2 for safety reasons. Such subjects will undergo the dose reduction and modified escalation procedure described in Section 7.2.2 in order to return to a 300 mg QD regimen. Alternatively, they may be discontinued from the study.

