6.10 Treatment for Dosing Reactions: Pharmacological and Supportive Therapy

Treatment for allergic reactions during the study is guided by the type of symptoms and severity as determined by the investigator.

- Treatment for acute reactions should be provided according to the standard of allergy care, with an antihistamine and/or epinephrine, along with IV fluids, a beta-agonist (eg, albuterol, by inhaler or nebulizer), oxygen, and/or glucocorticosteroids, as indicated.
 - Many mild acute allergic reactions can be transient and self-limiting, requiring no therapeutic intervention. Others, however, may require treatment. Generally, for mild symptoms requiring treatment, the subject should receive antihistamines.
- Acute allergic reactions manifesting with moderate symptoms will generally require therapeutic intervention, although some, even moderate, symptoms may on rare occasion be so transient as to require no specific treatment. Generally, for moderate symptoms requiring treatment, the subjects should receive antihistamines and/or

- ARC008 Protocol Amend 6.0
- epinephrine, as indicated. If there is uncertainty as to the severity of the reaction, administering epinephrine would be considered the most appropriate course of action.
- Generally, severe symptoms will require treatment. This will usually consist of antihistamines and/or epinephrine, as indicated. If there is uncertainty as to the severity of the reaction, administering epinephrine would be considered the most appropriate course of action.

The procedures that should be implemented after treatment of a reaction to an AR101 dose during the study are summarized in Table 11. An explanation follows the table.

Table 11: Procedures Following Treatment of a Dosing Reaction

Treatment Given for Reaction	Procedures Following Treatment
≤ 2 doses of antihistamines	Continue dose escalation if in Initial Escalation / Up-Dosing Period
Epinephrine: > 2 doses either in clinic or at home	Subject returns to clinic, undergoes Early Discontinuation visit, discontinues treatment
Epinephrine: single dose given in clinic	 Stop dosing at clinic Reduce next dose by 2 dose levels and administer in clinic Continue biweekly escalation
Epinephrine required for a second consecutive time during, or after, 1 escalation attempt	 Reduce next dose by 2 dose levels and administer in clinic Reduced dose level continued for 6 to 8 weeks Escalation may be attempted after 6 to 8 weeks

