Epinephrine required for a third consecutive time during an escalation attempt	Discontinue dosing Subject returns to clinic 14 days after last dose for Early Discontinuation visit
Epinephrine: single dose at home	Not counted in the total count of epinephrine uses unless severe anaphylaxis has occurred
	Reduce next dose by 1 or 2 dose levels and administer in clinic under medical supervision prior to resuming any dosing at home

• Antihistamines Given

If a subject receives 2 or fewer doses of antihistamines only, the dose escalation can be continued. If more than 2 doses of antihistamine, or epinephrine, or a combination of medications, is administered, then a different course of action is to be taken.

If symptoms during up-dosing at the study site or at home require > 2 doses of antihistamine alone or in combination with other medications (except epinephrine), reduce the next dose of study product by 1 or 2 dose levels and give it at the study site under medical supervision. If no symptoms occur at the reduced dose, continue up-dosing for the 2-week dosing interval.

ARC008 Protocol Amend 6.0

• Epinephrine – General Procedures

Any reaction to study product (in clinic or at home) that requires more than 2 doses of epinephrine will stop all further dosing of study product for the individual. The subject will be asked to return 14 days following the last dose of study product for an Early Discontinuation visit (Section 4.4).

• Epinephrine – Single Dose Administered at Clinic

If a single administration of epinephrine is required during, or after, a dose escalation in the clinic, no further dosing of study product is to occur at that visit. The next dose of study product is to be reduced by 2 dose levels and administered at the study site, but biweekly dose escalation should continue.

If a single administration of epinephrine is required for a second consecutive time during or after 1 escalation attempt, the dose should be reduced by 2 dose levels and the same dose level continued for 6 to 8 weeks. After 6 to 8 weeks at the reduced dose, an escalation may be attempted in the clinic.

If a single administration of epinephrine is required for a third consecutive time during an escalation attempt, no further dosing should be attempted and dosing will be discontinued. Subjects will be asked to return 14 days following their last dose of study product for an Early Discontinuation visit (Section 4.4).

• Epinephrine – Home

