If a single administration of epinephrine is given during dosing at home, this epinephrine use is not counted as one of the uses described above unless severe anaphylaxis occurred at home. Administration of epinephrine outside of the clinic should be followed immediately by the subject being taken to the nearest emergency department. The next dose of AR101 is to be reduced by 1 or 2 dose levels and administered in the clinic under medical supervision prior to resuming any dosing at home.

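### After home epinephrine for a reaction to a non-daily AR101 dose, protocol Sections 6.10, 6.9.5 and 6.8.2 do not fit together on dose amount and regimen

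*Protocol*

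**What the plan says.** Section 6.10 sets its scope broadly: "The procedures that should be implemented after treatment of a reaction to an AR101 dose during the study are summarized in Table 11". For one epinephrine dose given at home, the table and the text beneath it state: "The next dose of AR101 is to be reduced by 1 or 2 dose levels and administered in the clinic under medical supervision". Neither names a regimen or study period. The explanatory text for epinephrine given in the clinic is narrower, applying where a single administration "of epinephrine is required during, or after, a dose escalation in the clinic".

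Section 6.9.5 introduces Table 10 for subjects on 300 mg QD, QOD, BIW, QW or QOW, and in the same paragraph says: "Dose adjustment after administration of antihistamines and/or epinephrine for allergy symptoms related to dosing is described in Section 6.10". The QD row of Table 10 points to the up-dosing procedures. The non-daily row is different: "hold the scheduled dose until the AE is resolved and the dose can be safely administered", then reset the interval once the following dose is tolerated. A hold of more than 3 days needs discussion with the medical monitor. The text after the table says: "However, for subjects on nondaily regimens, the following guidelines and procedures apply". It then adds: "For subjects having acute reactions to QOD, BIW, QW, or QOW doses, the next action will be determined by symptom severity".

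Under 3.1.1, Table 10 and 6.9.5, transfer from Pathway 1 to Pathway 2 (with discontinuation as the alternative) follows one related SAE, one related severe AE, two related moderate AEs on separate occasions, or three consecutive doses judged not tolerated. Table 10 also permits transfer at any time for impaired tolerability.

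Section 6.8.2 treats a mild reaction that needed one dose of epinephrine as not tolerated. It requires transfer to Pathway 2, or allows withdrawal, once a non-daily regimen is not tolerated.

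**The concern.** Take a non-daily subject with a first, non-serious, mild or moderate reaction at home, treated with one dose of epinephrine. No transfer trigger in 3.1.1 or 6.9.5 has been met, yet the subject falls under 6.10 because of the treatment and under 6.8.2 because of the tolerability judgement. The three sections use different criteria and lead to different next doses and regimens.

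The immediate stake is safety: the question arises just after a reaction that needed epinephrine. There is also a consequence for the data. Epinephrine use and AEs leading to a change in treatment regimen are primary endpoints (protocol Section 2, Table 1). SAP Section 6.3 repeats the overall TEAE summary and the rescue-medication summary by daily and non-daily regimen, classified by the regimen first assigned in ARC008. If sites resolve the conflict differently, a mixture of practices ends up in the non-daily subgroup. The documents do not allow the size of that effect to be estimated.

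**Working it through.** No statistical figure is at issue. The check sets the sections side by side for the case above.

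| | 6.10 and Table 11, home epinephrine | Table 10 and 6.9.5, non-daily | 6.8.2 |
|---|---|---|---|
| Acts on | Treatment given | Severity, seriousness and number of reactions | Tolerability; one epinephrine dose makes even a mild reaction not tolerated |
| Next dose | 1 or 2 levels lower | No amount stated for a hold of up to 3 days; after a longer hold, options include 300 mg or about half | Follows from Pathway 2 if transferred |
| Place | Clinic | Study site in options 1 and 2; otherwise not stated | Study site, after a home dose suspected not tolerated |
| Regimen | Not addressed | Non-daily unless a trigger is met or the investigator chooses to transfer | Transfer required, or withdrawal allowed, once the regimen is not tolerated |

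**Dose amount.** Section 6.10 does not say which ladder defines a level for a non-daily subject. I assume Table 4, the ladder for subjects who leave a non-daily regimen: 80, 120, 160, 200, 240, 300 mg. Table 5 has the same top steps.

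- 1 level down: 240 mg; (300 − 240)/300 = 20% lower.
- 2 levels down: 200 mg; (300 − 200)/300 = 33% lower.
- 6.9.5 option 2: about half of 300 mg, or about 150 mg; about 50% lower.
- Pathway 2 restart: 160, 120 or 80 mg daily; 140/300 = 47%, 180/300 = 60% and 220/300 = 73% lower.

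The 6.10 step (20% to 33%) does not overlap the reduced doses written for non-daily subjects (47% to 73%).

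**Way back to 300 mg.** Section 3.4.1 says the maintenance regimen "is a 300 mg dose to be administered at the dosing interval that the subject last tolerated" in a previous sponsor study. Section 5.1 supplies maintenance as 300 mg sachets, and the Figure 8 schematic for temporary reductions is labelled for QD regimens only. Option 2 does return to 300 mg, after up to three half doses, but it is offered after a hold of more than 3 days and is not a 1- or 2-level step. Stepwise re-escalation for these subjects is described only through Pathway 2, which ends at 300 mg daily. Nothing says how a QW or QOW subject given 240 or 200 mg returns to 300 mg on that schedule.

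**Regimen.** Section 6.8.2 refers intolerance of a non-daily regimen to Table 9, which classifies tolerability by the symptoms a dose elicits. It does not say whether one dose that was not tolerated is enough. Read that way, it requires transfer after one event; 3.1.1 and 6.9.5 make transfer mandatory after three consecutive such doses or another listed trigger.

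**The case against.** The strongest reply is that 6.9.5 supplies the link itself. The paragraph above Table 10 names the non-daily regimens and sends dose adjustment after epinephrine to 6.10. Table 10 would then govern when to dose again and 6.10 how much and where. On timing this works, and it rules out a flat contradiction. It does not settle the amount or the regimen: the step it imports matches none of the non-daily reduced doses and leads to no described way back.

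Three stronger readings are tempting and are not supported.

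- A reader might infer that Table 10 tells non-daily subjects to resume 300 mg on schedule. It states no amount and resets the interval. Continuing 300 mg on the same schedule appears only in 6.9.5 option 1a, after a hold of more than 3 days, medical-monitor discussion and a tolerated supervised dose. That option also resets the interval, in a list that is expressly not exhaustive.
- A reader might infer that the choice is between full strength at home and a reduced dose in the clinic. Section 6.8.2 already asks for a supervised next dose after a home dose suspected not tolerated, so on place it agrees with 6.10.
- A reader might extend the conflict equally to epinephrine given in the clinic. That Table 11 row is not limited in its heading, but its explanatory text is tied to dose escalation, so its reach to a non-daily maintenance dose is unclear.

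It is also fair to say that a reduced dose within Pathway 1 is not impossible. Section 5.5 lets the investigator adjust a dose that is not tolerated, option 2 gives a reduced dose in the same pathway, and transfer is allowed at any time. The gap is a missing route for the step that 6.10 requires.

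**Conclusion.** The point holds for one epinephrine dose given at home after a reaction to a non-daily dose, where no listed transfer trigger has been met. For that event the documents can be read to lead to 240 or 200 mg in the clinic, to a hold with no reduced amount stated, to supervised 300 mg or about 150 mg after a hold of more than 3 days, or to a Pathway 2 restart at 80, 120 or 160 mg daily. The conflict is on dose amount and regimen only.

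The 240 and 200 mg figures rest on applying the Table 4 ladder, which the protocol does not expressly assign to subjects still on a non-daily regimen; that absence is part of the problem. The 20% to 33% reductions describe the instruction and are not an estimate of any effect on an endpoint. Neither the number of non-daily subjects nor the number of such events is given. The passages should be reconciled because this is a safety instruction and the correction is cheap. The documents give no basis for saying here which rule is right.

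**What to change.** Reconcile Sections 3.1.1, 6.8.2, 6.9.5 with Table 10, and 6.10 with Table 11:

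- Mark which Table 11 rows, and which paragraphs of 6.10, apply only to daily or escalating regimens.
- In Table 10 and 6.9.5, give one instruction for a non-daily dose followed by epinephrine, covering next dose, place of dosing, regimen and, if a reduced dose is kept, the return from it.
- State in 6.8.2 whether one dose that was not tolerated makes a non-daily regimen not tolerated, and align this with the trigger list.

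The clinical team chooses the content. The cost is wording in two tables and their text, with the approvals that any amendment needs under Section 11.1.

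SAP Sections 1.1 and 7.7 indicate that the study has ended and the database is locked, so the wording change would serve a successor protocol. For this study, the report could describe the next dose and regimen after each such event, using the dosing and adverse event listings already planned in SAP Sections 9.1 and 9.11.

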7 STUDY VISITS

Enrollment and study procedures are summarized in the following subsections.

A study physician must be available at all times during the in-clinic dosing visits and food challenges.

Enrollment and study procedures may be affected by a pandemic, epidemic, or other emergency not related to the study as described in Appendix 12.

7.1 Treatment Pathway 1

7.1.1 Screening/Baseline Visit

Before any unique ARC008-related procedures are performed, the investigator or designee must obtain written informed consent/assent for this study from the subject and parent/guardian (as applicable), as described in Section 11.2. The Screening/Baseline visit occurs on the same day (+3 days) as the exit visit of the parent study unless specified

otherwise in the parent study protocol, and must be completed within 28 days after the signing of the informed consent form (ICF)/assent form. Initiation of AR101 treatment in this study must be within 3 days after the Exit visit of the parent study for subjects treated with AR101 in the parent study, unless specified otherwise in the parent study protocol. The first dose of AR101 in ARC008 should not be administered on the same day as an exit food challenge or dosing in the parent study.

The following Screening/Baseline procedures will be conducted as part of ARC008 if not completed at the parent study Exit visit (or other visit if specified). A detailed list of Screening/Baseline procedures to be performed as part of ARC008 based on each parent study is provided as a guide in Appendix 1. Certain Screening/Baseline procedures must be repeated if last completed outside the windows specified in Appendix 1.

- Inclusion/exclusion criteria review
- Demographics
- Medical and allergy history review
- Concomitant medication review
- Food allergen exposure update
- Complete physical examination, including weight and height
- Vital signs
- PEF (should be measured at approximately the same time of day at each visit assessment [eg, morning, afternoon, evening])
- Blood sample collection:
 - Complete blood count (CBC)
 - Immunology assessments
- Serum pregnancy test (for sexually active females of childbearing potential only)
- SPT
- Completion of questionnaires:
 - ACT/C-ACT (for subjects with known asthma only) (complete before PEF)
 - TNSS (for subjects with known allergic rhinitis only)
 - FAQLQ and FAIM

The following procedures will be performed before discharge from the clinic:

- AE recording (including allergic symptoms)
- Peanut allergy training
- In-clinic dosing, unless the visit occurs on the same day as an exit food challenge or dosing in the parent study
- AR101 dispensing
- Home dosing instruction (Section 5.2)

Telephone contact: Site staff will contact the subject or subject's parent/caregiver by telephone 6 to 7 weeks after this visit to monitor compliance with AR101 dosing, enquire if any AEs (including allergic symptoms, GI symptoms, and accidental/nonaccidental food allergen exposure) occurred after the subject left the clinic, and to provide assistance in recording and management of events.

